### 3.3. Sample size justification

As this is a FIH exploratory Phase I/II study, no formal sample size has been calculated.

## Statistical Analysis Plan

Sponsor:	Gyroscope Therapeutics		
Protocol:	GT005-01 (FOCUS)		
Document Version No.:	04.0	Document Date:	17-JUN-2024

### 3.4. Subject disposition

The following summaries will be included in the disposition table considering all enrolled patients: number and percent of patients who are enrolled into the study, failed screening, treated, discontinued the study prior to or at the study week of the analysis (including reasons for discontinuation) by treatment dose, route of administration and overall.

A listing of patients who discontinue from the study prior to the end of study will be provided by treatment dose and route of administration. The listing will identify date, study day and the reason of study discontinuation.

Patients who sign an informed consent form and who are subsequently found to be ineligible prior to study treatment will be considered a screen failure. Screen failure information will not be summarized but only listed.

Number and percent of enrolled patients who were excluded (i.e., not evaluable) from SAF or FAS will be presented. A listing of patients and the reason of exclusion from corresponding analysis set will also be presented.

### 3.5. Demographic and baseline characteristics

Demographics and baseline ocular characteristics for the study eye will be summarized with descriptive statistics for the FAS by dose, route of administration and overall. Demographic characteristics will include age, gender, race, ethnicity and CFI rare variant subgroup. Baseline ocular characteristics for the study eye will be additionally summarized by CFI variant subgroups per route of administration. Ocular baseline characteristics include:

- Study eye selection (left eye OS or right eye OD)
- Best corrected visual acuity BCVA (in ETDRS letters)
- Low-luminance visual acuity LLVA (in ETDRS letters)
- Low-luminance deficit (BCVA-LLVA, in ETDRS letters)
- GA lesion area (mm^2) as assessed by FAF
- GA contour (Unifocal, Multifocal) as assessed by FAF
- GA foveal involvement (Foveal, Extrafoveal) as assessed by FAF and OCT
- Junctional zone pattern (Atypical, Banded, Diffuse, Focal, Cannot Grade) as assessed by FAF
- Drusen area (mm^2) as assessed by CFP
- Presence of hard drusen (Yes, No, Cannot Grade) as assessed by CFP
- Maximum drusen size within ETDRS Grid (Large, Intermediate, Small, Cannot Grade) as assessed by CFP
- Presence of reticular pseudodrusen (Yes, No, Cannot Grade) as assessed by OCT
- Presence of soft drusen (Yes, No, Cannot Grade) as assessed by CFP
- Presence of calcified drusen (Yes, No) as assessed by CFP

## Statistical Analysis Plan

Sponsor:	Gyroscope Therapeutics		
Protocol:	GT005-01 (FOCUS)		
Document Version No.:	04.0	Document Date:	17-JUN-2024

- Presence of cuticular drusen (Yes, No) as assessed by CFP
- CSFT ( $\mu\text{m}$ ) as assessed by OCT
- Years since GA diagnosis

### 3.6. Medical history

Medical history and current medical conditions for SAF will be listed for ocular (both study eye and fellow eye) and non-ocular events. No summary table will be produced.

### 3.7. Efficacy analyses

Efficacy analyses will be conducted using the FAS by treatment dose and route of administration.

**GA area (mm^2)** change from baseline in the study eye as assessed by FAF will be presented in spaghetti plots and in a summary by visit table. It will also be summarized in a table and line plots as least-squares means with 95% CI by visit using MMRM model with fixed effects for treatment (defined as dose and route of administration), study visit, baseline GA area (mm^2), treatment by visit interaction and visit by baseline GA area interaction.

**Square root of GA area (mm)** change from baseline in the study eye will be presented in spaghetti plots and in a summary by visit table. It will also be summarized in a table and line plots as least-squares means with 95% CI by visit using MMRM model with fixed effects for treatment, study visit, square root of baseline GA area (mm), treatment by visit interaction and visit by square root of baseline GA area (mm) interaction. MMRM analysis will be repeated for CFI rare variant subgroups and [REDACTED] by replacing in the model treatment with subgroups of interest.

For MMRM analysis an unstructured covariance matrix will be used to model the within-patient error. If an MMRM model with an unstructured covariance matrix does not converge, a more restricted covariance matrix can be considered in the following order until convergence is reached: first-order autoregressive, Toeplitz, compound symmetry and variance components.

Additionally, scatter plots with linear trend lines for square root of GA area size (mm) change from baseline at the target analysis visit vs. last observed CFI levels before the target analysis visit in the vitreous and aqueous samples will be generated by treatment groups.

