
Abbreviations: BCVA=best corrected visual acuity; CNV=choroidal neovascularisation; ETDRS=early treatment diabetic retinopathy study chart; FA=fluorescein angiography; LLVA=low luminance visual acuity; MAIA=macular integrity assessment; MNRead=Minnesota low vision reading; OCT=optical coherence tomography; OCT-A=optical coherence tomography angiography; Tel=telephone; [REDACTED].
 
1. Dependent upon location and Sponsor approvals, a Surgical Site may also act as a Local Site2. Screening assessments may be conducted over several days. The screening period may be extended up to a maximum of 12 weeks, if agreed by the Sponsor Medical Monitor. If the screening period is extended past the original 8-week screening period (8–12 weeks), standard ophthalmic exam, haematology/biochemistry, and visual acuity (BCVA/LLVA) assessments should be repeated. In the event the GT005 administration is deferred during the surgical procedure (e.g., due to an AE occurring during surgery) the screening period may be extended up to 16 weeks if agreed by the Sponsor Medical Monitor. Additionally, if the screening period is extended past 12 weeks (12–16 weeks), in case of GT005 deferral, standard ophthalmic exam, haematology/biochemistry, visual acuity (BCVA/LLVA), and FAFs will be repeated.3. Pre-surgery assessments should be performed within 7 days prior to surgery.4. Visit 3 will take place at the surgical site, however this may be held at the local site if more practical.5. A pre-surgery ocular safety check will be performed to verify no new adverse events that could halt surgery. [REDACTED]7. Other imaging modalities may be performed to assess for CNV if OCT-A is not available. In the event that the OCT/OCT-A images are inconclusive to rule out the presence of CNV the subject will be required to undergo an additional assessment via FA. At the Investigator's discretion, FA may also be performed initially prior to the OCT/OCT-A results being available, but this is not mandatory.8. OCT-A and/or fluorescein angiography may be performed during the study period if clinically indicated, for example, if a subject converts to wet AMD.9. Microperimetry should be performed during scheduled visits at sites with a MAIA microperimeter: Microperimetry will be performed at either screening or prior to surgery (within the screening visit window) and may be performed over >1 day if needed. If in the view of the Investigator, the subject is not capable of performing the test, this will not be considered an exclusion to study participation. Microperimetry assessment instructions will be provided in the imaging manual.10. If omitted at screening, assessments should be performed during the pre-surgery visit. [REDACTED]12. LLVA is not performed at Visits 3, 4 and 4.1.13. A visual acuity check using ETDRS or Snellen chart (near card is permissible) must be performed on the study eye if >4 weeks have lapsed since the last BCVA with ETDRS assessment. If Snellen result is >3 lines (BCVA equivalent to 15 letters) worse than the previous BCVA ETDRS score, then a BCVA with ETDRS assessment must be repeated. If the BCVA ETDRS score in the study eye is either >15 letters worse than the previous BCVA ETDRS score or <24 letters score (Cohorts 4 to 7), the surgery must be postponed pending discussion and approval by the Sponsor Medical Monitor. [REDACTED]15. Enrolled subjects will be asked if they are willing to consent to have historical FAF and/or OCT images that were obtained within 1 year prior to enrolment, if available, provided to the sponsor.	

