4.3. Exclusion Criteria

Subjects must not enter the study if any of the following exclusion criteria are fulfilled:

1. Have evidence or history of CNV in the study eye. Subjects are permitted to have CNV in the fellow eye defined as either:
 - a. Non-exudative/sub-clinical fellow eye CNV identified at screening, or

- b. Known history of fellow eye CNV with either ≥ 2 years since diagnosis or with no active treatment required in 6 months prior to screening
- 2. Presence of moderate/severe non-proliferative, diabetic retinopathy or worse in the study eye
- 3. Have history of vitrectomy, sub-macular surgery, or macular photocoagulation in the study eye
- 4. History of intraocular surgery in the study eye within 12 weeks prior to Screening (Visit 1). [REDACTED]
- 5. Have clinically significant cataract that may require surgery during the study period in the study eye
- 6. Presence of moderate to severe glaucomatous optic neuropathy in the study eye; uncontrolled IOP despite the use of more than two topical agents; a history of glaucoma-filtering or valve surgery is also excluded
- 7. Axial myopia of greater than -8 diopters in the study eye
- 8. Have received any investigational product for the treatment of GA within the past 6 months or 5 half-lives (whichever is longer), other than nutritional supplements such as the age-related eye disease study (AREDS) formula
- 9. Have received a gene or cell therapy at any time
- 10. Have a contraindication to the specified protocol corticosteroid regimen
- 11. Are unwilling to use two forms of contraception (one of which being a barrier method) for 90 days post-dosing, if relevant
- 12. Active malignancy within the past 12 months, except for: Appropriately treated carcinoma in situ of the cervix, non-melanoma skin carcinoma, or prostate cancer with a stable prostate-specific antigen (PSA) ≥ 12 months
- 13. Have any other significant ocular or non-ocular medical or psychiatric condition which, in the opinion of the Investigator, may either put the subject at risk or may influence the results of the study
- 14. Cohorts 5 to 7 only: presence of metallic objects or implanted stimulator devices in or near the head, including cochlear implants, deep brain stimulators, vagus nerve stimulators, and other implanted electrodes or stimulators

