## 2. SUBJECT POPULATIONS

### 2.1. Population definitions

The **All Enrolled Set** includes all patients who signed informed consent. This analysis set will be used to summarize patient disposition and for summaries of successful GT005 and BSS delivery rates of SDS orbit device.

The **Safety Analysis Set (SAF)** will include all subjects who have undergone surgery and received GT005. The SAF will be used for analysis of safety and laboratory data.

The **Full Analysis Set (FAS)** will include all subjects in SAF who have baseline and at least one post baseline value of GA area size via FAF in the study eye. The FAS will be used for analysis of efficacy data.

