### 2.2. Protocol deviations

Protocol deviations will be identified and recorded by the study monitor in the Monitoring Visit Reports and/or the electronic data capture (EDC) system. Prior to locking the database for the analyses supporting clinical study reports, the relevant important protocol deviations will be identified. They will be classified as CSR non-reportable or CSR reportable based on their effect on the rights, safety, or wellbeing of the subjects and/or the quality and integrity of the data. CSR reportable protocol deviations will be summarized for SAF. The CSR reportable protocol deviations based on SAF will be provided in a listing.

No exclusions of patients from SAF and FAS will occur due to protocol deviations.

Alternative treatment for GA in the study eye during long-term follow up is not prohibited in the protocol but cannot be excluded. In this case efficacy and assay variables will be censored at last observation prior to the start of the alternative treatment. The censoring of data in such cases will be derived from concomitant medication data.

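### Study-eye FAF area measured after conversion to wet AMD is by default analysed as GA growth; add one supportive GA-area run without those values, and keep every planned analysis

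*SAP*

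**What the plan says.** **Entry.** Protocol 4.3, criterion 1, excludes subjects who "Have evidence or history of CNV in the study eye". Protocol 1.1 names neovascular AMD and GA as the two morphological sub-types of late AMD.

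**Follow-up.** Protocol Table 2, footnote 8, reads: "OCT-A and/or fluorescein angiography may be performed during the study period if clinically indicated, for example, if a subject converts to wet AMD". Table 3, footnote 4, and the visit lists in Protocol section 7 make the same provision. No conversion rate is given.

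**Analysis sets.** The FAS requires a baseline and at least one post-baseline FAF area in the study eye, with no condition on CNV. SAP 2.1 adds: "The FAS will be used for analysis of efficacy data". SAP 2.2 adds: "No exclusions of patients from SAF and FAS will occur due to protocol deviations".

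**Censoring.** SAP 2.2 has one rule. Its trigger is: "Alternative treatment for GA in the study eye during long-term follow up is not prohibited in the protocol but cannot be excluded". Its effect is: "In this case efficacy and assay variables will be censored at last observation prior to the start of the alternative treatment". Neither CNV onset nor treatment given for CNV is named.

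**GA analysis.** SAP 3.7 says of GA area that "change from baseline in the study eye as assessed by FAF will be presented in spaghetti plots and in a summary by visit table". It adds an MMRM for GA area, and plans the same outputs for square-root GA area. Treatment in the models is dose combined with route. SAP 3.2 relies on MAR for missing GA values and mentions no post-treatment event.

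**Acuity.** BCVA, LLVA and low-luminance deficit are summarised in SAP 3.9.2, under Safety.

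**The concern.** The GA analysis is meant to describe atrophy growth. The protocol treats CNV as a different disease state and keeps it out of the study eye at baseline. Once an eye converts, a change in its measured FAF area may reflect CNV or its treatment as well as atrophy. The sponsor already accepts the principle in SAP 2.2, where a post-treatment event that makes later values unrepresentative leads to censoring. Conversion is an event of the same kind and has no visible rule.

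The point estimates and intervals are the whole message of this study, because SAP 3.1 plans no hypothesis tests. They also have several uses. Protocol 11.3.2 compares GA area with historical natural progression, and Protocol 11.3 allows interim results to inform development decisions. The same square-root values feed the CFI-subgroup MMRM and the scatter plots against CFI levels in SAP 3.7. In a small cell one converted eye could create or hide an apparent dose or route difference, and nothing beside the least-squares mean would say so.

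**Working it through.** **1. Sizes.** Protocol 3.1 gives cohort maxima of 5 for each of Cohorts 1 to 3, 20 for Cohort 4, 5 for each of Cohorts 5 and 6, and 20 for Cohort 7. The sum is 3×5 + 20 + 2×5 + 20 = 65, which reproduces the stated enrolment of about 65. A dose-by-route cell can be as small as 3 to 5, if an escalation dose is not taken into expansion. It can reach 5 + 20 = 25, if an expansion cohort uses a single dose.

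**2. Shift in a cell mean.** One eye with spurious change D moves the raw mean of n eyes by D/n. D is an assumption, since the documents give no value.

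| n | D = 1 mm² | D = 2 mm² | D = 4 mm² |
|---|---|---|---|
| 3 | 0.33 | 0.67 | 1.33 |
| 5 | 0.20 | 0.40 | 0.80 |
| 20 | 0.05 | 0.10 | 0.20 |
| 25 | 0.04 | 0.08 | 0.16 |

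D/n is exact for the by-visit table. For the MMRM least-squares means, which adjust for baseline, it is a guide.

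**3. Square-root scale.** The shift in mm depends on lesion size: [√(A + D) − √A]/n. I take A at the entry limits for Cohorts 1 to 6 (1.25 and 17.5 mm²) and D = 2 mm².

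- A = 1.25: √3.25 − √1.25 = 1.803 − 1.118 = 0.685 mm, so 0.137 mm at n = 5 and 0.034 mm at n = 20.
- A = 17.5: √19.5 − √17.5 = 4.416 − 4.183 = 0.233 mm, so 0.047 mm at n = 5 and 0.012 mm at n = 20.

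**4. Size against sampling error.** With one shifted value the expected variance is SD² + D²/n, and the 95% half-width is about t × √(variance/n). I assume SD = 1 mm².

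- n = 5, no converter: 2.776 × √(1/5) = 1.24 mm².
- n = 5, D = 2: 2.776 × √(1.8/5) = 1.67 mm². The 0.40 shift is 0.40/1.24 = 32% of the undisturbed half-width; for D = 1 the figure is 0.20/1.24 = 16%.
- n = 20: 2.093 × √(1/20) = 0.47 mm², rising to 2.093 × √(1.2/20) = 0.51 mm² for D = 2.

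These are intervals from a single cell's own data. The MMRM as described has one covariance matrix, so there the extra variance would be shared across cells.

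**5. Chance of meeting the problem.** P(at least one converter) = 1 − (1 − p)ⁿ. For assumed risks of 2%, 5% and 10% this is 10%, 23% and 41% in a cell of 5, and 73%, 96% and 99.9% among 65.

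**6. Could a visible rule remove the values?** The FAS definition, the no-exclusion rule, the GA-treatment censoring rule and the missing-data section were each checked. None mentions conversion. FAF area recorded at a scheduled visit after conversion therefore enters the by-visit tables and both MMRMs.

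**The case against.** The strongest reply has four parts.

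- **The trial is descriptive.** It is first in human and unpowered, so no formal conclusion can flip. Sampling error in a cell of 5 already exceeds the shift in the example. This stands, and it limits the weight of the point.
- **Much can be traced already.** SAP 3.9.1 tabulates study-eye TEAEs by dose and route, efficacy values and concomitant treatments are listed, and spaghetti plots show each eye. A conversion recorded as an AE would be counted. This stands in part: the reader would have to cross-check listings, and no estimate without the affected values is planned.
- **Retention is an inference.** The AESI list and parts of the SAP are redacted, and the imaging manual may say how the central reader grades a converted eye. This stands. The claim concerns visible text only.
- **Conversion may itself be an effect of treatment or surgery.** Dropping later values conditions on a post-treatment event. This is why the planned analysis must stay and the added run can only be supportive.

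The documents do not support four stronger readings that a reader might draw:

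- **That the protocol expects conversions.** It foresees them as a contingency, with OCT-A or FA only if clinically indicated.
- **That acuity after conversion should also be removed.** BCVA and LLVA are secondary functional outcomes, but SAP 3.9.2 summarises them under Safety. Vision lost after conversion is a harm that must be counted.
- **That conversion differs by route.** This is possible, but no figure bears on it.
- **That a cell whose two results differ should be declared uninterpretable.** In a cell of 3 to 5 eyes, dropping any eye changes the estimate, and there is no principled threshold.

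**Conclusion.** The concern holds for GA area. The visible SAP has no rule for study-eye conversion, although the protocol excludes CNV at entry and foresees its onset. Post-conversion FAF area is by default reported as GA growth. The effect is potentially material in cells of about 3 to 5 eyes and minor at 20 to 25. These sizes rest on assumed values of D, SD and conversion risk, and on the assumption that conversion alters measured FAF area at all. The documents quantify none of these. The change is worth making because it is cheap and follows the sponsor's own censoring principle. It does not invalidate the planned analysis, and it does not reach the acuity summaries.

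**What to change.** Keep all planned analyses, and keep every BCVA, LLVA and low-luminance-deficit value in the safety summaries. Then add to SAP 3.7:

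1. **A conversion date for the study eye:** the first visit at which CNV is documented by imaging or recorded as an AE.
2. **One supportive run** of the GA area MMRM and the square-root GA area MMRM, with study-eye values set to missing from that visit onward.
3. **A footnote** beside the least-squares means giving the number of converters by dose and route.
4. **Side-by-side presentation** of the two results. Where they differ materially, the CSR should caution that the cell's estimate reflects more than GA growth. No automatic rule is needed.

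If the database is already locked, the CSR should label the run as an addition.

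The cost is one rerun of existing programs, a conversion-date flag built from imaging and AE records, and a few values lost from the supportive run. That run has two weaknesses to state with it. It assumes MAR after conversion. It also depends on OCT-A or FA done only when clinically indicated, so some conversions may be dated late or missed.

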V3.0, 02 MAY 2019	
This protocol amendment includes: Revision of entry criteria to:
 
 include all eligible atrophic AMD patients: those with a rare variant resulting in CFI haploinsufficiency as well as those without a CFI variant. The requirement for low serum CFI has also been removed Clarify microperimetry requirement. At sites with a MAIA MP, all subjects will be assessed with a MP if feasible as assessed by the Investigator 	
GT005 has the potential to downregulate complement activation in all atrophic AMD, and there is no expectation that there would be differences in safety or tolerability in a broad atrophic AMD population; the two subpopulations will be analysed in the clinical endpoint analyses.
 
As there are a limited number of subjects to evaluate the functional outcome of retinal sensitivity, this revision allows for inclusion of all subjects who may reasonably complete the assessment.

	Addition of a blood plasma sample collection at Dosing (Visit 2), Week 5 (Visit 4), Week 36 (Visit 7) or at Early Termination.	[REDACTED]
	Addition of microperimetry assessment at Week 12 (Visit 5) and at the Early Termination Visit.	Due to the small sample size in the study, these additional assessments give opportunity to collect more microperimetry data.

Protocol Version	Change	Justification
	[REDACTED]	[REDACTED] [REDACTED] [REDACTED] [REDACTED] [REDACTED]
	[REDACTED]	[REDACTED] [REDACTED]
	Removed requirement to remain in medical facility overnight following surgery.	Emerging safety profile from the completed dose escalation in Part 1 of the study does not support need for overnight stay in a medical facility.
	Risk Section updated.	Updated risks to include those associated with topical steroid use. Added worsening of vision as a risk.
	[REDACTED]	[REDACTED] [REDACTED]
	Added (serious) adverse device effect language, device deficiency definitions and reporting requirements.	Inclusion of Orbit SDS medical device for Cohort 5 and 6 surgeries.
	Updated guidance on GT005 destruction.	Provide more detailed instruction and clarity.
	Throughout the document.	Inconsistencies removed and language clarified. As these are minor revisions, they have not been summarised.
V6.1/UK, 17 NOV 2020	Reference to the Orbit SDS medical device and Cohort 5-6 removed throughout protocol.	Cohort 5 and 6 which includes delivery using the Orbit SDS device will not be conducted in the UK at this time.

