#### 2.1.1. Subgroups of interest

Subgroup analyses will be performed for selected efficacy variables. The FAS can be stratified into two CFI variant subgroups: **CFI rare variant** subgroup of patients with rare variant resulting in CFI haploinsufficiency, and **Broad GA** subgroup including the rest of patients in the study;

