### 3. STATISTICAL METHODS

#### 3.1. General information

Two interim analyses and a clinical study report (CSR) are planned. First interim analysis will include data up to Week 72 from cohorts 1-4 with GT005 delivered via the transvitreal procedure. Second interim analysis will include data from cohorts 1-4 up to Week 96 and from Orbit SDS administration cohorts 5-7 up to Week 48. Clinical study report will be based on the analysis of all variables specified in this SAP from all 7 cohorts on data over 96 weeks.

All outputs will be incorporated into Word files and PDF files, sorted and labeled according to the International Conference on Harmonisation (ICH) recommendations, and formatted to the appropriate page size(s).

Tabulations will be produced for appropriate demographic, baseline, efficacy, biomarker assay, and safety parameters. For categorical variables, summary tabulations of the number and percentage within each category (with a category for missing data) of the parameter will be presented. For continuous variables, the number of observations, mean, median, quartiles, standard deviation, standard error (SE), minimum and maximum values will be presented. Where appropriate, 95% confidence intervals (CIs) for point estimates of the mean or proportion will be provided. Data will be listed and summarized using descriptive statistics by dose, by route of administration, and by assessment visits as appropriate. Efficacy and biomarker assay data will additionally be summarized by CFI rare variant and broad GA subgroups. All ocular evaluations and ocular adverse events, where appropriate, will be presented by eye (Study Eye, Fellow Eye).

No formal statistical hypothesis testing will be performed for this study.

Medical history, concurrent procedures and adverse events will be coded using the Medical Dictionary for Regulatory Activities (MedDRA). Prior and concomitant medications will be coded using World Health Organization (WHO) Drug Reference List dictionary version Mar 2020.

All statistical analyses will be performed using SAS statistical software (Version 9.4), unless otherwise noted.

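### The CFI subgroup MMRM replaces treatment with subgroup, so its LS means are unadjusted for dose and route and would carry any imbalance in them

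*SAP*

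**What the plan says.** SAP 2.1.1 splits the efficacy population by genotype: "The FAS can be stratified into two CFI variant subgroups". One is the "subgroup of patients with rare variant resulting in CFI haploinsufficiency"; the other, Broad GA, is everyone else.

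SAP 3.7 fits its first GA area MMRM with "fixed effects for treatment (defined as dose and route of administration), study visit, baseline GA area" and the visit interactions. The square-root version has the same structure, ending with "treatment by visit interaction and visit by square root of baseline GA area (mm) interaction". For the CFI subgroups the square-root model is then repeated "by replacing in the model treatment with subgroups of interest".

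SAP 3.1 bases the clinical study report on data "from all 7 cohorts on data over 96 weeks", which means all dose levels and both delivery routes. The same section rules out formal hypothesis testing. The planned output is LS means with 95% confidence intervals by visit.

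**The concern.** Because treatment is defined as dose and route, replacing it removes both. What remains is subgroup, visit, square-root baseline area, subgroup-by-visit and visit-by-baseline. No dose, route, cohort or site term is left, and the SAP text available describes no other subgroup model that contains both factors.

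Balance cannot be assumed. Protocol 3.1 fills dose and route through sequential cohorts, with the Orbit route at US sites only. Protocol 6.6 describes an open-label study, and no randomised or CFI-stratified assignment to dose or route is described. Entry criteria also differ by cohort (Protocol 4.2): BCVA limits differ between Cohorts 1 to 3 and Cohorts 4 to 7, and Cohort 7 has no upper lesion-size limit. As background only, the Version 3.0 entry in the amendment history widened enrolment to "include all eligible atrophic AMD patients: those with a rare variant resulting in CFI haploinsufficiency as well as those without a CFI variant". The rare-variant share could therefore have changed over the life of the study.

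At stake is how the genotype result will be read. Protocol 1.1 suggests that patients with CFI haploinsufficiency may do better on GT005. Side-by-side subgroup curves will be read against that idea, although each curve reflects its own subgroup's mix of doses and routes.

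**Working it through.** The documents state no effect size, standard deviation or subgroup count for this analysis, so there is no plan figure to reproduce for the subgroup contrast. The one check available is the enrolment total: 3×5 + 20 + 2×5 + 20 = 65, as stated.

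**Bias formula.** At a single visit, leaving baseline area aside, the unadjusted contrast (rare variant minus Broad GA) with no true subgroup effect is

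Σ over groups t of (share of rare-variant subjects in t − share of Broad GA subjects in t) × mean growth in t.

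It is zero if the two subgroups are spread identically over the groups, or if growth is the same in every group.

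**Illustration.** The group sizes are the enrolment caps in Protocol 3.1: Part 1 n = 15, Cohort 4 n = 20, Orbit cohorts n = 30. Two inputs are assumed, not taken from the documents: the rare-variant share in each stratum, and a Part 1 growth excess of 0.05 to 0.20 mm (square-root scale) over the other two. The three strata are stand-ins for dose/route groups. With only Part 1 differing, the bias is (Part 1 share among rare-variant subjects − Part 1 share among Broad GA subjects) × growth excess.

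| Rare-variant share: Part 1 / Cohort 4 / Orbit | Part 1 share, rare variant | Part 1 share, Broad GA | Difference | Spurious contrast, mm | SE ratio, adjusted to unadjusted |
|---|---|---|---|---|---|
| 20 / 20 / 20% | 3/13 = 0.2308 | 12/52 = 0.2308 | 0 | 0.000 | 1.00 |
| 50 / 20 / 20% | 7.5/17.5 = 0.4286 | 7.5/47.5 = 0.1579 | 0.2707 | 0.014 to 0.054 | 1.04 |
| 80 / 20 / 10% | 12/19 = 0.6316 | 3/46 = 0.0652 | 0.5664 | 0.028 to 0.113 | 1.27 |
| 100 / 20 / 10% | 15/22 = 0.6818 | 0/43 = 0 | 0.6818 | 0.034 to 0.136 | 1.57 |

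With the stratum term kept beside subgroup, the contrast is 0.000 in every row. If Part 1 grew more slowly than the rest, the signs would reverse.

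**Precision.** With p the rare-variant share in a stratum, the SE ratio is √{[1/Σ n p(1−p)] / [1/n(rare) + 1/n(broad)]}.
- 50/20/20%: Σ = 3.75 + 3.2 + 4.8 = 11.75. The ratio is √(0.0851/0.0782) = 1.04.
- 80/20/10%: Σ = 2.4 + 3.2 + 2.7 = 8.3. The ratio is √(0.1205/0.0744) = 1.27.
- 100/20/10%: Σ = 0 + 3.2 + 2.7 = 5.9. The ratio is √(0.1695/0.0687) = 1.57.

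**Model size.** There are seven post-baseline FAF visits to Week 96 (Weeks 5, 12, 24, 36, 48, 72 and 96). Five dose-by-route groups are assumed.
- Main treatment model: 7×5 + 7 = 42 fixed parameters.
- Subgroup model as planned: 7×2 + 7 = 21.
- Adding treatment as a main effect: 21 + 4 = 25.
- Adding treatment-by-visit as well: 7×(5 + 1) + 7 = 49.

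**The case against.** The strongest reply is that nothing shows an imbalance. No document gives CFI status by cohort, and with equal shares the bias is exactly zero. The output is also descriptive, in an exploratory study with no sample size calculation. SAP 3.5 already summarises CFI rare-variant status by dose and route, and ocular baseline characteristics by CFI subgroup within route, so a reader could see an imbalance if there is one. All of this stands. It limits the point to interpretation and leaves the size open. It does not supply an adjusted estimate: a baseline table can show an imbalance but does not remove it from the LS means.

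A reader might infer from the amendment history that rare-variant subjects sit mainly in early, lower-dose, transvitreal cohorts, and so predict the direction of the bias. The documents do not support that. They do not say how many subjects were enrolled before Version 3.0. Part 1 covers all three doses, and the doses used in Cohorts 4 and 7 are left open. A link with the transvitreal route is plausible; a link with low dose is weaker.

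Two textual defences fail. The opening line of SAP 3.7, which places efficacy analyses by dose and route, could suggest separate fits, but the specific sentence substitutes subgroup into the pooled model. The SAP document history mentions removal of a subgroup analysis, but current sections 2.1.1, 3.1 and 3.7 still plan the CFI subgroups.

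**Conclusion.** The point holds as a matter of model specification: the CFI subgroup LS means are unadjusted for dose and route, and assignment to these was not randomised. Whether this distorts the comparison depends on two unknowns, the spread of CFI status over dose/route groups and the growth difference between those groups. Both must be non-zero for bias to arise. The range of 0 to 0.136 mm rests entirely on the assumed shares, the assumed growth excess and the enrolment caps. It shows scale and is not an estimate.

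The consequence is for descriptive reading only; no error rate is affected. Nor should a reader infer that an adjusted model would show which genotype responds better. Every subject receives GT005 and the subgroup MMRM uses study eyes only. Without an untreated group, a genotype difference in growth still mixes treatment response with natural progression.

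**What to change.** In the subgroup MMRM of SAP 3.7, keep treatment (dose and route) as an additive main effect alongside subgroup, visit, subgroup-by-visit, square-root baseline area and visit-by-baseline. Report subgroup LS means at the observed treatment margins. If the planned model is shown as well, label its LS means as unadjusted for dose and route, and read them with the CFI-by-dose and route summary already planned in SAP 3.5.

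The cost is one SAP sentence, about four parameters under the five-group assumption (21 to 25) and wider intervals. In the assumed scenarios the subgroup standard error rises about 4% under mild imbalance and 27 to 57% under severe imbalance. A large rise is itself informative, because it means the data can barely separate genotype from treatment.

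The additive term assumes that the dose/route shift is the same in both subgroups and at every visit. Adding treatment-by-visit would relax the second assumption but takes the model to 49 fixed parameters with about 65 subjects at most, so it is not the main proposal. Cohort differences within the same dose and route, such as the BCVA entry limits, would remain unadjusted.
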